2.2 Study Duration, Enrollment and Number of Participants

Participant commitment will consist of at least two and a half hours over a 4-month period (two hours to take the *CRC Knowledge Survey*, watch the videos and take the *Post Video CRC Knowledge Survey* and thirty minutes to complete the *30 Day Follow Up CRC Knowledge Survey*). Participants willing to take part in a qualitative one-on-one interview will commit an additional hour, totaling three and a half hours over a 6-month period. The entire study is expected to last 12 months. We intend to enroll a total of 60 participants. However, in order to recruit the necessary 20 for the qualitative interview, we may need to enroll more than 60 since not everyone participating in *Study Days 1 and 2* will choose to participate in *Study Day 3*.

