3.2 Intervention/Treatment procedures

Study Day 1: Consented participants come to STM Church. During *Study Day 1*, they will be asked to complete the *CRC Knowledge Survey*, watch three CRC educational videos in Spanish and subsequently complete the *Post Video CRC Knowledge Survey* in Spanish. Both surveys will be administered on paper form.

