3.3 Follow- up procedures

Study Day 2: The participants return to STM Church 30 +/- 7 days after their participation in *Study Day 1*. During *Study Day 2*, they will complete the *30 Day Follow Up CRC Knowledge Survey* on paper form.

Study Day 3: A random subset of participants from *Study Days 1* and *2* will be invited to participate in qualitative one-on-one interviews aimed at identifying barriers preventing Latinos from participating in CCTs.

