3.4 Subject Completion/ Withdrawal procedures

At the completion of *Study Day 2*, participants will receive a \$100 gift card and a study T-shirt from either our research assistant or one of the volunteers, all of whom will be Tango trained and enlisted on the study's IRB. Participants interested in participating in qualitative one-on-one interviews aimed at identifying barriers preventing Latinos from participating in CCTs will be invited to participate in *Study Day 3*. Following completion of *Study Day 3*, these participants will receive an additional \$50 gift card for their participation in the qualitative one-on-one interviews. Participants choosing to withdraw from the study may do so at any point by notifying the PI via email.

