4.4 Methods

Primary Endpoint: Twenty enrolled participants will participate in qualitative, semi-structured, one-on-one interviews that will be performed in Spanish. The interviews will be recorded and transcribed.

ATLAS.ti software will be used for the transcript analysis. The top 2 conceptual themes within each section of the interview (attitudes regarding general clinical trials, attitudes regarding CCTs, and perception of the Hispanic/Latino community) and the top 3 higher-level, holistic themes across the sections will be reported in terms of percentage of participants.

Secondary Endpoint 1: Use of repeated measures ANOVA with appropriate follow-up contrasts to compare total number of correct responses within three time points (baseline vs post-video; baseline vs 30 +/- 7 days follow-up; post-video vs 30 +/- 7 days follow-up) accounting for multiple observations within participants. Knowledge pertaining to CRC symptoms will be assessed using the “Knowledge of Warning Signs” questions from the “Bowel Cancer Awareness Measure”. Potential answers include “Yes”, “No” and “Don’t Know”. The overall score will range from 0 to 9 and it is anticipated that average scores will increase after the intervention. Higher scores imply a greater knowledge of symptoms.

Secondary Endpoint 2: Use of repeated measures ANOVA with appropriate follow-up contrasts to compare total number of correct responses within three time points (baseline vs post-video; baseline vs 30 +/- 7 days follow-up; post-video vs 30 +/- 7 days follow-up) accounting for multiple observations within participants. Knowledge pertaining to CRC risk factors will be assessed using the “Knowledge of Risk Factors” questions from the “Bowel Cancer Awareness Measure”. This scale is measured using a Likert 1-5 scale with “1” corresponding to “Strongly Disagree” and “5” corresponding to “Strongly Agree”. The overall score will range from 11 to 55 and it is anticipated that the average scores will increase after the intervention. Higher scores imply higher knowledge of risk factors.

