Secondary Endpoint 3: Use of repeated measures ANOVA with appropriate follow-up contrasts to compare total number of correct responses within three time points (baseline vs post-video; baseline vs 30 +/- 7 days follow-up; post-video vs 30 +/- 7 days follow-up) accounting for multiple observations within participants. Knowledge of CRC screening and general facts will be assessed using nine questions from the “Colorectal Cancer Decision Quality Instrument (CRC-DQI)”. The overall score will range from 0 to 9 and it is anticipated that average scores will increase after the intervention. Higher scores imply greater knowledge of screening and facts.

Secondary Endpoint 4: Since questionnaires will be completed pre and post video, we will explore, in a preliminary fashion, the association between watching the video (X) and willingness to participate in CCTs (Y) using repeated-measures/mixed-effects logistic regression on the paired responses of participants. The mediating effect of *Study Day 1* post-video health knowledge levels (M) on the relationship between X and Y (established in the preliminary step above) will be explored. Using a structural equation modeling approach, two mixed-effects generalized linear models will be carried out: one model uses both X and M to predict Y, while another uses only X to predict M. The two

models will be compared and tested using the algorithm introduced by Imai and colleagues^{50,51} The estimated average causal mediation effect (from X to Y, through M) will be tested using the bootstrapping method with 1,000 replications, and the proportion of the effect being mediated will be reported as the effect size. Lastly, in order to explore an adjusted approach, the same steps used for the mediation model will be replicated, while incorporating demographic variables as covariates.

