4.5 Sample Size and Power

A traditional “power analysis” is not directly applicable to the primary endpoint of the study which is qualitative in nature. Based on published methodologies to assess the adequate sample to reach “saturation”,⁵²⁻⁵⁴ we chose to invite 20 participants for qualitative interviews.

For our quantitative, secondary endpoints, a traditional “power analysis” was performed. A total of 60 participants will be recruited into the study. If in our study population the mean difference is 0.4, which as defined by Cohen is a small to medium difference, and the pre- to post- correlation is 0.5, then the power to reject the null hypothesis will be over 80%. If the differences in our study population are more extreme, our sample size will have even more power to reject the null hypothesis.

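### Endpoints 1-3: repeated-measures ANOVA has no analysis set or missing-survey rule; run complete-case, it discards the Day-1 pair of anyone who misses Day 30, and a mixed model on all available scores would keep it

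*Combined protocol and SAP*

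**What the plan says.** Section 4.4 (Methods) gives the same analysis for Secondary Endpoints 1, 2 and 3, and item B of the synopsis analytic plan repeats it: "Use of repeated measures ANOVA with appropriate follow-up contrasts to compare total number of correct responses within three time points". The contrasts are baseline vs post-video, baseline vs Day 30 and post-video vs Day 30, "accounting for multiple observations within participants". No section defines who is analysed or how a missing survey is handled.

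The three surveys come from two visits. On Study Day 1 (section 3.2) participants complete the baseline survey, then "watch three CRC educational videos in Spanish and subsequently complete the" post-video survey, so both scores come from one session. The third survey needs a separate visit (section 3.3): "The participants return to STM Church 30 +/- 7 days after their participation in" Study Day 1. Section 3.4 adds: "Participants choosing to withdraw from the study may do so at any point".

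Section 4.5 bases power on 60 participants and a difference of 0.4: if "the pre- to post- correlation is 0.5, then the power to reject the null hypothesis will be over 80" per cent. It makes no allowance for loss. Section 2.2 says that "in order to recruit the necessary 20 for the qualitative interview, we may need to enroll more than 60"; the reason given is filling the interviews, not replacing missed surveys. Mixed-effects models appear only under Secondary Endpoint 4: "repeated-measures/mixed-effects logistic regression on the paired responses of participants".

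**The concern.** Classical repeated-measures ANOVA works on participants with a score at every time point. A standard routine (AnovaRM in statsmodels), given data with some Day-30 scores missing, refused them as unbalanced. The usual way round this is to drop incomplete participants. That would remove someone who completed both Day-1 surveys from the contrast that uses only those two surveys, because of a visit about a month later.

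Baseline vs post-video is the most direct measure of what the videos do. Two things are at stake for it: precision, because pairs already collected go unused, and validity, if those who return gained more or less than those who do not. There is also a freedom-of-choice problem. The text allows either a complete-case ANOVA or paired comparisons on available pairs, the two can give different estimates, and nothing fixes the choice before the data are seen.

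**Working it through.** **Inputs.** From section 4.5: 60 participants, difference 0.4 (read as standardised, since the text refers to Cohen), pre-post correlation r = 0.5. Not in the documents and therefore assumed: two-sided alpha 0.05, Day-30 loss of 10, 20 or 30%, and the way return depends on scores.

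**Step 1: reproduce the stated power.** In SD units the SD of the paired difference is √(2(1 − r)) = √(2 × 0.5) = 1, so dz = 0.4/1 = 0.4. For n = 60 the noncentrality is 0.4 × √60 = 3.10 on 59 df, and power is 86.2%. This agrees with the stated figure of over 80%, with all 60 pairs analysed.

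**Step 2: complete-case power for baseline vs post-video.** The same formula applies with n equal to the number who return. The last column uses a pooled ANOVA error term with 2(n − 1) df, assuming equal correlations of 0.5 among the three scores. The 95% CI half-width is t(0.975, n − 1)/√n.

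| Assumed Day-30 loss | n analysed | Power, paired error | 95% CI half-width (SD) | Power, pooled error |
|---|---|---|---|---|
| none, or all Day-1 pairs kept | 60 | 86.2% | 0.26 | 86.7% |
| 10% | 54 | 82.3% | 0.27 | 83.0% |
| 20% | 48 | 77.5% | 0.29 | 78.3% |
| 30% | 42 | 71.6% | 0.31 | 72.6% |

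With the paired error term, 52 completers give 80.8% and 51 give 79.99%. With the pooled term, 51 give 80.8% and 50 give 79.97%. Power therefore falls below 80% at 9 missing of 60 (15%) or 10 of 60 (17%), depending on the error term.

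**Step 3: sensitivity of Step 2 (paired error).**
- One-sided 0.05: complete-case power is 90, 86 and 82% at 10, 20 and 30% loss, against 92% with all pairs.
- r = 0.4, 20% loss: 70% against 79%. r = 0.6, 20% loss: 86% against 93%.
- More enrolled: 65 with 20% loss leaves 65 × 0.8 = 52 completers, 81% against 89%. 75 with 30% loss leaves 75 × 0.7 = 52.5, taken as 52, 81% against 93%.

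**Step 4: bias in the complete-case gain.** This is a large-sample simulation with a true gain of 0.40 SD, r = 0.5, equal SDs, and return following a logistic model in the Day-1 scores.

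| Return depends on | 10% loss | 20% loss | 30% loss |
|---|---|---|---|
| both Day-1 scores equally (log-odds 0.5 or 1 per SD) | 0.40 | 0.40 | 0.40 |
| baseline 0.5 and post-video 1 per SD | 0.42 | 0.44 | 0.46 |
| one score only, 0.5 to 1 per SD, either sign | 0.35 to 0.45 | 0.31 to 0.49 | 0.27 to 0.53 |

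The first row shows no bias because, with equal SDs, the sum of the two scores is uncorrelated with their difference. Selecting on overall knowledge therefore leaves the mean gain alone. Bias appears only when return is associated with the gain.

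**Step 5: what a mixed model does.** In a simulated data set with 60 enrolled and 48 returning, a REML fit with unstructured covariance gave the same baseline vs post-video estimate and standard error as the paired analysis of all 60 (0.3459, SE 0.1336). One data set shows that the two estimators coincide; it says nothing about average bias. For baseline vs Day 30, at an assumed difference of 0.4 SD with 54, 48 and 42 returning, simulated power was 83.2, 79.1 and 74.8% with the mixed model against 82.7, 77.4 and 71.5% complete-case: a gain of about 1 to 3 points.

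**The case against.** The plan never says incomplete participants will be deleted. The phrase about multiple observations within participants, and the joint label used for Endpoint 4, may mean the authors treat repeated-measures and mixed-effects as interchangeable terms. Paired tests on available pairs also fit the text and lose no Day-1 pair. This stands: the defect is an unstated rule whose usual default is poor, and the harm is conditional on that default.

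Loss may also be small. The follow-up is a half-hour survey at the same church, and section 3.4 pays the $100 card only after Study Day 2. With up to 8 of 60 missing, power stays above 80% under Step 2, and at one-sided 0.05 it does so even at 30% loss. This stands too. A reader might infer that the power claim in section 4.5 fails; without a loss rate, an alpha or a sidedness in the documents, that is not shown.

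A reader might also infer that any link between scores and return biases the gain, or that the gain will be overstated. Step 4 does not support either: equal dependence on both scores gives no bias, and dependence on one score can push the estimate in either direction.

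Finally, one sentence saying that each contrast uses everyone with both surveys scored would protect baseline vs post-video equally well. That is a fair minimum repair. The mixed model does the same, adds a little for the Day-30 contrasts, and keeps one model for the overall time test and all three contrasts.

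**Conclusion.** The point holds as a low-cost improvement to the secondary analyses. Endpoints 1-3 have no analysis set or missing-survey rule, and the named method in its standard form discards Day-1 pairs already collected when Day 30 is missed.

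If that form is used, the cost in power for baseline vs post-video is about 4, 9 and 15 percentage points at an assumed 10, 20 and 30% loss (two-sided 0.05, paired error). Bias is possible but needs return to be associated with the gain; its size and direction cannot be read from the documents. Enrolling beyond 60 could offset the loss of power but would not remove such bias. The qualitative primary endpoint is not touched.

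**What to change.** In section 4.4 (Secondary Endpoints 1-3) and in item B of the synopsis analytic plan, replace repeated-measures ANOVA with text to this effect:

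*Each score will be analysed with a linear mixed model for repeated measures using all available survey scores, with time as a three-level factor, an unstructured within-participant covariance, REML estimation and a small-sample degrees-of-freedom correction such as Kenward-Roger. The overall test of time and the three pairwise contrasts will be reported, with the number of participants observed at each time point. The two contrasts involving Day 30 assume that missing Day-30 scores are missing at random.*

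The cost is a change of text and analysis code: same data, same contrasts, no added visits or participants, and no assumed loss rate to write in. There are two small downsides. With complete data the contrasts equal paired tests, so they may differ slightly from ANOVA contrasts that use a pooled error term. The model also does not say how to score a survey with skipped items, which section 7 permits; that needs its own rule.

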
Safety Evaluations
 <hr/> 
Statistical And Analytic Plan
	
N/A, this study imposes minimal risk.
 <hr/> 
A. Identification of Barriers: The top 2 conceptual themes within each section of the interview (attitudes regarding general clinical trials, attitudes regarding CCTs, and perception of the Hispanic/Latino community) and the top 3 higher-level, holistic themes across the sections will be reported in terms of percentage of participants.
 
B. Assessment of the potential impact of the educational videos in Spanish on CRC knowledge: Use of repeated measures ANOVA with appropriate follow-up contrasts to compare total number of correct responses within three time points (baseline vs post-video; baseline vs 30 +/- 7 days follow up; post-video vs 30 +/- 7 days follow-up) accounting for multiple observations within participants.
 
C. Exploration of the potential relationship between an increase in health knowledge of a specific cancer via educational videos in Spanish and willingness to participate in CCTs: Since questionnaires will be completed pre- and post-video, we will explore, in a preliminary fashion, the association between watching the video (X) and willingness to participate in CCTs (Y) using repeated-measures/mixed-effects logistic regression on the paired responses of participants. The mediating effect of Study Day 1 post-video health knowledge levels (M) on the relationship between X and Y (established in the preliminary step above) will be explored. Using a structural equation modeling approach, two mixed-effects generalized linear models will be carried out: one model uses both X and M to predict Y, while another uses only X to predict M. The two models will be compared and tested using the algorithm introduced by Imai and colleagues. The estimated average causal mediation effect (from X to Y, through M) will be tested using the bootstrapping method with 1,000 replications, and the proportion of the effect being mediated will be reported as the effect size. Lastly, in order to explore an adjusted approach, the same steps used for the mediation model will be replicated, while incorporating demographic variables as covariates.

--	---

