2 INVESTIGATIONAL PLAN

2.1 Study Design

Type of Design: Single-arm intervention study

Brief Overview of Study Phases: Following completion of the Hispanic Masses at STM Church on Saturday and Sunday, attendees will be approached by members of our study team and CHWs. They will be screened for their eligibility to participate in our study through an Intake Form which they will be able to complete either in-person while they are at the Church, or through the project website. Those deemed eligible will be prompted to complete the RIS online, in-person, or via the phone. Those that complete the RIS and enroll in the study will be scheduled to come to STM Church on future *Study Days*. During *Study Day 1*, participants will complete the *CRC Knowledge Survey*, watch three CRC educational videos in Spanish and then complete the *Post Video CRC Knowledge Survey*. On *Study Day 2* (30 +/- 7 days after their participation in *Study Day 1*), participants will return to STM Church in order to complete the *30 Day Follow Up CRC Knowledge Survey*. Subsequently, on *Study Day 3*, 20 of the 60 participants will participate in a one-on-one qualitative interview aimed at identifying barriers preventing Latinos from participating in CCTs.

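### Mediator M is defined only by its post-video value, so as written the model of M on X cannot be estimated or has slope 0 (minor; exploratory analysis)

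*Combined protocol and SAP*

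**What the plan says.** Section 2.1 Study Design gives the design: "Type of Design: Single-arm intervention study". Every participant watches the videos, so there is no unexposed group.

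For Secondary Endpoint 4, section 4.4 Methods first relates watching the video (X) to willingness to join a cancer clinical trial (Y), "using repeated-measures/mixed-effects logistic regression on the paired responses of participants". It then turns to mediation by knowledge. Both section 4.4 and item C of the synopsis's statistical plan define the mediator in the same terms; section 4.4, referring to Study Day 1, reads "post-video health knowledge levels (M) on the relationship between X and Y (established in the preliminary step above) will be explored". Two mixed-effects generalized linear models follow: "one model uses both X and M to predict Y, while another uses only X to predict M". The average causal mediation effect is tested with 1,000 bootstrap replications, and the proportion mediated is the effect size.

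Neither place gives M a value on the pre-video record. Elsewhere the wording differs: section 1.5 Secondary Objectives and section 11 Plans for Publication speak of a rise in knowledge rather than a post-video level.

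The same knowledge questionnaire is given in all three surveys (section 1.4 Relevant Literature and Data, Questionnaire), and Study Day 1 includes it both before and after the videos (section 3.2).

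**The concern.** A mediated effect needs the mediator to be able to differ between the two levels of the exposure. Here the two levels are the two records of the same person: before the videos (X=0) and after them (X=1). A mediator that exists only after the videos has no counterpart at X=0, so the model of M on X has nothing to compare.

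At stake are the two quantities that depend on that model: the average causal mediation effect and the proportion mediated. They bear on the second secondary objective in section 1.5, and section 11 names the mediating effect among the results to be published. A slope that is missing, or exactly 0 with no residual variation, would probably be noticed when the model is fitted. The practical risk is therefore less a false null in print than a mediator that is redefined after the data have been seen.

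**Working it through.** **The plan's own figure.** The documents give no power or precision for the mediation step. The only figure is in section 4.5 Sample Size and Power: "If in our study population the mean difference is 0.4" and "the pre- to post- correlation is 0.5, then the power to reject the null hypothesis will be over 80" percent, with 60 participants. It reproduces. I take 0.4 as a standardised difference and assume a two-sided alpha of 0.05, which is not stated:

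- SD of the paired difference, in units of the score SD: sqrt(2 × (1 − 0.5)) = 1, so the standardised paired difference is 0.4 / 1 = 0.4.
- Noncentrality: 0.4 × sqrt(60) = 3.10, with 59 degrees of freedom.
- Power: 86.2% (noncentral t). One-sided it would be 92.2%. Both exceed 80%.

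This figure does not involve M and is untouched by what follows.

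**The model of M on X.** Inputs: a single arm (section 2.1), paired pre- and post-video records (section 4.4), and M equal to the Study Day 1 post-video score (section 4.4 and synopsis item C). Write pre_i and post_i for participant i's two Study Day 1 scores, and M = a + bX for the fixed part of the model.

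1. *Post-video records only.* X = 1 on every row. The columns (1, X) are identical, so the 60 × 2 design matrix has rank 1 of 2 and b cannot be estimated.
2. *Post-video score on both records.* b = mean(post) − mean(post) = 0 for any data. The predicted distribution of M is the same at X=0 and X=1, so the mediation effect is 0. The proportion mediated is 0 divided by the total effect, which is 0 if the total effect is not itself 0. Every bootstrap replication gives b = 0, because the identity holds within each participant.
3. *Change score, post_i − pre_i, as one value per participant.* The argument is the same: no slope on post-video rows, and mean(change) − mean(change) = 0 on both rows. It would work only if the pre-video record were given a change of 0, which is again a value for each occasion and is not stated.
4. *Score at each occasion.* M = pre_i at X=0 and post_i at X=1. Then b = mean(post) − mean(pre), the average gain, which is estimable.

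**Numerical check.** This used 60 simulated participants, with an assumed score SD of 4, a true gain of 1.6 (0.4 SD) and a pre-post correlation of 0.5.

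| M taken as | Result for b |
|---|---|
| Post-video rows only | rank 1 of 2, no slope |
| Post-video value on both rows | 0; all 1,000 bootstrap slopes 0; residual variance collapses to about 0 |
| Score at each occasion | 1.42 (SE 0.46; bootstrap 95% interval 0.51 to 2.35) |

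The values in the last row are illustrative. The first two rows hold for any data.

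**What survives.** With the post-video score on both rows, the outcome model has columns (1, X, M), which are of full rank whenever scores differ between participants. On post-video rows only, X drops out but M can still be estimated. The term for M in the outcome model therefore remains. The preliminary model of Y on X does not use M at all.

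**The case against.** The strongest reply is that no passage tells the analyst to use post-video rows only or to copy the post-video score onto the pre-video row. The paragraph speaks of questionnaires before and after the video, of paired responses and of mixed-effects models. Read as a whole, it points to knowledge measured at the same occasions as Y. The reference to Study Day 1 may serve only to separate the immediate post-video survey from the 30-day one. The references elsewhere to a rise in knowledge also suggest that the pre-video score was meant to enter.

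Much of this stands. A score at each occasion is the likeliest intention, which is a main reason for the low rating. But the text goes further than leaving M open: in two places it defines M as the post-video level, and that definition does not work with the model it specifies. Nor do the references to a rise in knowledge settle the matter, since a single change score fails too.

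A reader might infer that the second secondary objective is lost, or that no planned analysis would connect knowledge with willingness. The documents do not support that: the outcome model keeps its term for M, so an association between knowledge and willingness can still be estimated, and Secondary Endpoint 4 as listed in section 4.3 concerns watching the videos and willingness, not mediation. A reader might also set the 0 slope against the 0.4 in section 4.5, as if the plan forecast a path of that size. Section 4.5 does not name the outcome to which 0.4 applies, so that contrast is not the plan's own.

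**Conclusion.** The point holds as a minor error of definition in an exploratory analysis. With M as written, the slope of M on X is unestimable or exactly 0, and the mediation effect and proportion mediated are undefined or 0 whatever the data show. This is algebra. It rests only on the single-arm design, on X varying solely between a participant's two Study Day 1 records, and on M having one value per participant. It needs no assumption about effect size or correlation.

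Confidence is high that the definition and the stated model do not fit together. That is not a prediction that the analysis will fail in practice, because the analyst may well use the workable reading. The preliminary video-willingness model, the M term in the outcome model, the primary endpoint, Secondary Endpoints 1-3 and the stated power are not affected.

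**What to change.** In section 4.4 (Secondary Endpoint 4) and in item C of the synopsis's statistical plan, replace the definition of M with: M is the knowledge score at the same Study Day 1 occasion as Y, namely the pre-video score at X=0 and the post-video score at X=1. A single change score should not be used in its place.

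The cost is one sentence in two places. No new data, visit or participants are needed, because the same questionnaire is already completed before and after the videos. The change should be made before the responses are analysed, so that the choice of mediator does not follow from the results.
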